5.1 Description

The Orbera (Apollo Endosurgery, Austin, TX) is an elastic spherical balloon made of silicone, filled with 550 mL of saline solution, and is FDA approved for weight loss in adult US patients with body mass index between 30 to 40 kg/m². The deflated balloon comes preloaded on a catheter, which is blindly advanced trans-orally into the stomach. An endoscope is then advanced alongside it to ensure accurate placement of the balloon in the fundus. Under direct visualization, the balloon is then inflated by injecting saline solution through the external portion of the catheter. The Orbera balloon is currently used in many countries outside the United States and is typically implanted for 6 months and then retrieved endoscopically.

5.2 Method for Assigning Subjects to Treatment Groups

All enrolled subjects will get the Orbera intragastric balloon.

5.3 Preparation and Administration/Implantation of Investigational Device

The intragastric balloon will be used as described by the Orbera PMA application approved by the FDA, in adolescents who meet this protocol eligibility criteria described in Sections 4.1 and 4.2. See Section 5.1 for description of implantation.

[name], Co-PI, has performed multiple studies with the Orbera balloon placement and was part of the pivotal trial. He will be physically supervising the endoscopic placement for all study subjects. [name], PI, has 7 years of clinical experience (3 years of fellowship training and 4 years as a staff pediatric gastroenterologist), including performing endoscopic procedures. He will be receiving required course training through the manufacturing company upon approval of the study.

5.4 Subject Compliance Monitoring

The Orbera IGB will be advanced to the stomach under endoscopy guidance and inflated with approximately 600 ml of normal saline. Subject transient nausea and pain symptoms will be managed with few days course of antiemetic and antispasmodics as per our clinical practice. Subject and their parents will then receive a phone call by a GI nurse at 4 days after the procedure (\pm 1 day), then 2 weeks (\pm 1 week), at 1 month (\pm 1 week), and monthly thereafter (\pm 1 week) when not being seen for a physical exam and in the weight management clinic at months 3, 6, 9, and 12 (\pm 1 week), per the clinical protocol visit schedule for the IGB as indicated on Table 2. The PI will evaluate all subjects if the GI nurse feels they need to be evaluated based on results of telephone questionnaire.

At 6 months (\pm 1 week), the subject will return for balloon removal at the pediatric endoscopy unit under monitored pediatric anesthesia care. During this visit, the subject will have blood samples drawn; a physical exam by pediatric gastroenterologist ([name]) or pediatric endocrinologist ([name]), followed by a meeting in the weight management clinic with the dietitian. Following the blood samples, PE, and WMC, the balloon will be removed at the same visit using the standard balloon retrieval kit approved by the FDA.

After balloon removal, all subjects will continue to be followed by the weight management team as indicated on Table 2. Weight, height, waist circumference, and demographic information will be collected at baseline, 3 months (\pm 1 week), time of balloon removal (6 months \pm 1 week), 9 months (\pm 1 week), and at 12 months (\pm 1 week).

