3.1 General Design

Potential subjects will be seen by a pediatric endocrinologist ([name]) or a pediatric gastroenterologist ([name]) who will review and approve the potential subject's inclusion and exclusion criteria. For interested subjects who have met all the inclusion and exclusion criteria, assent will be obtained from the subject and consent will be obtained from the parent/legal guardian. After consent, the subject will be given three questionnaires to complete at home and return at the baseline visit; the PN Q will be returned to and reviewed by the dietitian in the weight management clinic (WMC), and the CES-D and SCAS will be returned to and reviewed by the psychologist.

At baseline, subjects will be seen by the pediatric weight management multidisciplinary team consisting of a pediatric endocrinologist ([name]) or a pediatric gastroenterologist ([name]) for a physical examination; a registered dietitian in the WMC; and a psychologist. Blood, urine, and stool samples will be collected at baseline. Food record templates will be provided to study subjects to be completed for three days prior to each future WMC visit.

The baseline requirements may all be completed in one day, or they may be completed on separate days depending on scheduling times and the subject's availability. Female subjects will also have a urine pregnancy test in the morning before the procedure.

If the subject still meets all the inclusion and exclusion criteria after the baseline evaluations and the pregnancy test are completed, s/he will undergo physical examination followed by placement of the IGB by a gastroenterologist ([name] or [name]) via endoscopic approach under monitored and controlled anesthesia. Esophagogastroduodenoscopy (EGD) is very safe and routine diagnostic approach for adolescents with gastrointestinal disorders.[25] The balloon will remain in the stomach if tolerated for 6 months, and then it will be removed endoscopically by a gastroenterologist ([name] or [name]). In order to prepare for the IGB removal, the subject will need to be on a liquid diet for 48 hours prior to its removal, and consume nothing by mouth for at least 12 hours prior to the IGB removal. Subjects will be informed that the risk for complications increases after 6 months and that it is imperative that the balloon is removed at 6 months, otherwise the subject assumes the additional risks.

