6.7 Removal of Balloon after 6 months by PI or Co-PI

The balloon will remain in the stomach if tolerated for 6 months, and then it will be removed endoscopically by a gastroenterologist ([name] or [name]). In order to prepare for the IGB removal, the subject will need to be on a liquid diet for 48 hours prior to its removal, and consume nothing by mouth for at least 12 hours prior to the IGB removal.

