4-Female subjects will have a urine pregnancy test in the morning before the IGB insertion. Once the pregnancy test is confirmed negative, then the IGB can be inserted. At this visit, the subject will also be given a wallet card with emergency information, as well as Mayo Clinic brochures regarding the upper endoscopy and intragastric balloon for weight loss.

5-At the 6 month visit, the subject will have blood samples drawn; a physical exam by the pediatric endocrinologist ([name]) or a pediatric gastroenterologist ([name]); and a meeting in the weight management clinic with the dietitian. Following the blood samples, PE, and WMC, the IGB will be removed at the same visit. The 6 month visit and balloon removal may all be completed in one day, or they may be completed on separate days depending on scheduling times and the subject's availability. This will be up to the discretion of the study team. In order to prepare for the IGB removal, the subject will need to be on a liquid diet for 48 hours prior to its removal, and consume nothing by mouth for at least 12 hours prior to the IGB removal.

6-Other tests include:

- CBC with differential
- Electrolytes panel (Sodium, Potassium, Calcium, Creatinine, Chloride, Bicarbonate, BUN)
- Liver function tests (AST, ALT, Alkaline phosphatase, Total Bilirubin, Total Protein, Albumin)
- Nutritional assessment (Fe/TIBC, B12, Folic Acid, 25-Hydroxy Vitamin D, Ferritin)
- Coagulation panel (ProTime/INR, PTT)
- Total Cholesterol/Lipid panel

- Thyroid function tests, PTH
- Insulin
- Glucose
- CRP
- HgA1c
- Urine sample

7-Questionnaires will be given to the subject after consenting to complete at home with a request that they be returned at the baseline visit. The PN Q will be returned to and reviewed by the dietitian at the weight management clinic. The CES-D and SCAS will be returned to and reviewed by the psychologist during the subject's psychological assessment. Any elevations in the CES-D and SCAS surveys will be further assessed during the subject's visit with the psychologist. If clinically indicated, additional psychological assessment and follow-up that may be needed and will be part of the subject's standard of care.

8-At the PE, the subject's height, weight, waist circumference, HR, BP, and demographics will be collected at baseline, 3, 6, 9 , and 12 months.

7 Statistical Plan

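### Month-6 weight, waist and fasting bloods can fall at the end of the 48-hour removal liquid diet, a condition no other measurement visit shares, and neither this nor the balloon's own mass is handled

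*Combined protocol and SAP*

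**What the plan says.** Section 5.4 has the subject return at 6 months (± 1 week) for removal, and sets the order of events: "Following the blood samples, PE, and WMC, the balloon will be removed at the same visit using the standard balloon retrieval kit approved by the" US regulator. The same section lists month-6 weight and waist at the time of balloon removal. Table 2 footnote 8 places these measurements at the physical exam.

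Section 6.7 gives the preparation, which sections 3.1 and Table 2 footnote 5 repeat: the subject must be "on a liquid diet for 48 hours prior to its removal, and consume nothing by mouth for at least 12 hours prior" to removal.

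Footnote 5 adds flexibility: "The 6 month visit and balloon removal may all be completed in one day, or they may be completed on separate days", and "This will be up to the discretion of the study team". It sets no order between the measurements and the start of the liquid diet.

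Section 3.1 asks for a fast of 8 to 12 hours before bloods at every visit. It states no liquid diet before baseline or months 3, 9 or 12.

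Section 3.2 sets the primary endpoint at 10% TBWL or more, without a time point. Section 3.3 names liver enzymes, fasting insulin, HgA1c and lipids. Section 2 lists sustained weight loss after removal as a specific aim. Section 7 plans t-tests or alternatives from baseline to each follow-up.

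**The concern.** A change between visits can be read as a treatment effect only if the measuring conditions are the same or the difference is known. Under the section 5.4 sequence, month 6 is measured after two days of liquids, and every comparison visit is measured on usual intake. Where the study team splits the visit, a subject may or may not be in preparation when weighed and bled. The plan does not ask for that status to be recorded.

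Month 6 closes balloon exposure and is the obvious reference for the sustainability aim. A short-term loss of gut content and water at that visit would be credited to the balloon, and its return would later look like regain. Fasting insulin and lipids could also respond to two days of altered intake, and that response could not be separated from six months of balloon treatment.

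**Working it through.** The plan gives no SD, power or sample-size formula, so there is no figure of its own to reproduce. What follows is a sensitivity check.

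**Inputs from the documents**
- Expected TBWL: 13.16% at 6 months and 11.27% at 12 months (section 1.5.3)
- Responder threshold: 10% (section 3.2)
- Subjects: 12 (section 7)
- Balloon fill: 550 mL (sections 1.2, 5.1) or about 600 mL (sections 1.4, 1.5.1, 5.4)

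**Assumptions, none of them in the documents**
- Preparation lowers scale weight by 0.5-2 kg.
- Baseline weight is 100-140 kg.
- SD of TBWL is 5-9 points, with 7 as the central value.
- SD of the within-subject change from month 6 to month 9 is 2-4 points.
- Saline weighs about 1 kg per litre.

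**1. Preparation effect alone.** Points of TBWL = 100 × kg / baseline kg.
- Smallest: 100 × 0.5/140 = 0.36
- Largest: 100 × 2/100 = 2.0

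**2. Saline offset.** Baseline is weighed without the balloon and month 6 with it, so the fill hides some loss.
- Smallest: 100 × 0.55/140 = 0.39 points
- Largest: 100 × 0.6/100 = 0.60 points

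**3. Net effect at 120 kg with 0.6 kg of saline (0.50 points)**

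| Preparation effect | Gross points | Net points |
|---|---|---|
| 0.5 kg | 0.42 | -0.08 |
| 1 kg | 0.83 | +0.33 |
| 2 kg | 1.67 | +1.17 |

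With 0.55 kg of saline the top value is +1.21, so the net range is about -0.1 to +1.2.

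**4. Sustainability reference.** The expected fall from month 6 to month 12 is 13.16 - 11.27 = 1.89 points. The net effect is about -5% (-0.1/1.89) to +63% (1.2/1.89) of that fall.

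**5. Responders, if month 6 is used.** P(TBWL ≥ 10) = Φ((3.16 + net)/7), with a true mean of 13.16 and SD 7.

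| Net points | P(≥ 10%) | Expected of 12 | Shift |
|---|---|---|---|
| 0 | 0.674 | 8.09 | none |
| -0.1 | 0.669 | 8.03 | -0.06 |
| +0.33 | 0.691 | 8.29 | +0.20 |
| +1.2 | 0.733 | 8.80 | +0.71 |

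**6. Planned test, baseline to month 6.** A two-sided paired t-test with n = 12 and a mean of 13.16 has power above 0.99 at SD 5, 7 and 9. A shift of about a point does not alter what it finds.

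**7. An apparent change from month 6 to month 9 when there is none.** This uses a two-sided paired t-test at 0.05 with n = 12 and noncentrality (net/SD) × √12. The probability of significance, for an SD of change of 2, 3 and 4 points, is:
- net 0.33: 0.08, 0.06, 0.06
- net 1: 0.35, 0.18, 0.12
- net 1.2: 0.48, 0.25, 0.16

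The plan does not list this test. The figures apply only if the sustainability aim is examined this way.

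**The case against.** The strongest reply is that the weight bias has no established direction. The balloon is still in place at the month-6 weighing, and by month 9 both the saline and any preparation effect are gone. If the preparation effect is about 0.6 kg or less, the two roughly cancel or the sign reverses. A liquid diet also need not mean sharp energy restriction, since its calories are not specified. This stands, and it rules out any claim that month-6 weight loss is inflated by a known amount. It does not make the conditions comparable. The fill is a roughly known mass that can be subtracted, whereas the preparation effect is unrecorded, and saline does nothing to correct bloods.

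Footnote 5 also stands in part. Same-day measurement is the section 5.4 sequence, but it is not certain for every subject. The footnote permits the remedy without requiring it.

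Three stronger readings are tempting and are not supported:
- **Month-6 loss is partly a preparation effect that reverses by month 9.** The documents give neither a size nor a reversal.
- **All metabolic change at month 6 is affected.** HgA1c would hardly move in 48 hours. Glucose and GI hormones are drawn but are not named endpoints.
- **The food record biases a result.** On a same-day visit about two of its three days ("Food record templates will be provided to study subjects to be completed for three days prior to each future WMC visit") are preparation diet. The record guides dietary advice, however, and has no endpoint or planned analysis.

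Finally, this is a largely descriptive pilot, and its planned test from baseline is robust to the problem. That limits the weight of the point but does not remove it.

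**Conclusion.** The concern holds as a lack of standardised measuring conditions at month 6, not as a demonstrated bias in one direction. Sections 5.4 and 6.7 together put month-6 weight, waist and fasting bloods at the end of a preparation that no other measurement visit has, and footnote 5 lets this vary between subjects.

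Under the stated assumptions the net effect on TBWL at 120 kg is about -0.1 to +1.2 points. At SD 7 that is between -0.06 and +0.71 of 12 responders, and up to about 63% of the expected 1.89-point fall to month 12. No size can be given for insulin or lipids. The exposure is to borderline responders if month 6 is the endpoint time, to month 6 as the reference for sustainability, and to diet-sensitive markers. The change is worth making because it is cheap and uses an option the protocol already has.

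**What to change.** The change concerns measurement timing and handling only. The preparation for removal stays as it is.

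1. In section 5.4 and Table 2 footnote 5, require month-6 weight, waist and fasting bloods to be taken before the removal liquid diet starts, using the separate-day option and the ± 1 week window. Record when the liquid diet began.
2. Record the fill volume at insertion (and at any replacement), and subtract its mass from weights taken with the balloon in place, at months 3 and 6. Without this step, earlier weighing alone would leave month-6 TBWL understated by 0.39-0.60 points. The stated fill volumes of 550 mL and about 600 mL also need to be reconciled.
3. Where a subject can be measured only on removal day, flag those values as taken under preparation, and show month-6 results with and without them.

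The cost is a wording change, two recorded items, and one extra trip for some families. No new test is needed.

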1.5.3 Potential Benefits

The Orbera intragastric balloon is expected to result in 12.3%, 13.16 and 11.27% total body weight loss (TBWL) at 3, 6, and 12 months after implantation, respectively, based on recent review.[18] This balloon is currently FDA approved for use in adults in the United States. Other potential benefits include improving the metabolic syndrome manifestation such as:

1. Sustainable decrease in baseline heart rate (>10 beats/min) and systolic blood pressure (>10 mmHg/hg)
2. Normalization of liver function panel
3. Decrease in fatty liver infiltration on liver ultrasound (US)
4. Decrease in Hg1Ac level

5. Improvement of fasting lipid profile
6. Increase in activity level

2 Study Objectives

Primary Objective:

Assess the safety and effectiveness of an intragastric balloon device in obese adolescent subjects with comorbidities to assist with weight reduction and reverse metabolic complications.

The intended use for the subject device (IGB) in adolescents is to induce > 10% total body weight loss in morbidly obese adolescents.

Specific Aims:

- Determine if placement of IGB for a period of 6 months is safe and results in weight loss and metabolic improvement in obese adolescents
- Determine if intragastric balloon is well tolerated by adolescents
- Determine if weight loss is sustainable after the IGB removal through integrating the subjects in the pediatric weight management program

Study Protocol Hypothesis:

Intragastric balloon is a safe, well tolerated and effective intervention for weight loss and decreasing obesity complications in adolescents with comorbidities.

3 Study Design

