3.2 Primary Study Endpoints

The primary endpoint will be achieving $\geq 10\%$ total body weight loss (TBWL).

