This is a pilot study of 12 subjects only, so results will be largely descriptive. Standard statistical analysis will be performed. We will use t-tests or alternative measures will be used to test whether weight loss was significant from baseline to each of the follow up points.

8 Safety and Adverse Events

All adverse events occurring during the study, including those not meeting the criteria of an Unanticipated Adverse Device Effect (UADE) will be recorded on the appropriate case report form. Records of these events will be maintained and reports submitted to the FDA and IRB according to the regulatory requirements. All adverse events will be reported. Expected clinical adverse events and anticipated adverse device effects are those listed in Section 1.5.2.

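### Month 3 and month 6 weights include the saline-filled balloon, later weights do not, and the plan makes no deduction: a small bias, conservative against baseline but favourable to any comparison of month 6 with months 9 or 12

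*Combined protocol and SAP*

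**What the plan says.** Footnote 8 to Table 2 (section 6.8) ties weight to the physical exam: "At the PE, the subject's height, weight, waist circumference, HR, BP, and demographics will be collected" at baseline and at months 3, 6, 9 and 12. Two places give the order of events at month 6. Section 5.4 says "Following the blood samples, PE, and WMC, the balloon will be removed at the same visit", and footnote 5 says "Following the blood samples, PE, and WMC, the IGB will be removed at the same visit". Footnote 5 adds "The 6 month visit and balloon removal may all be completed in one day, or they may be completed on separate days", but removal still follows the exam. Section 5.5 places months 9 and 12 after removal.

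Before removal, "the subject will need to be on a liquid diet for 48 hours prior to its removal" (section 6.7), followed by a fast of at least 12 hours.

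Section 7 will "test whether weight loss was significant from baseline to each of the follow up points". No section mentions subtracting the device or its fill.

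For the primary endpoint, section 3.2 says "The primary endpoint will be achieving" a TBWL of at least 10%, with no time point. The third specific aim in section 2 is "Determine if weight loss is sustainable after the IGB removal".

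The fill is 550 mL in sections 1.2 and 5.1, and about 600 mL in sections 1.4, 1.5.1 and 5.4. Section 5.8.3 names the serial number as the item matched to the subject, and Table 3 in section 9.3 has no row for the insertion procedure or the fill.

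**The concern.** The weight series mixes two measurement conditions. With the balloon in place the scale reads body plus saline; at baseline and after removal it reads body alone. The direction of the error is known, and averaging over subjects does not remove it.

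Its effect depends on the comparison:

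- **Baseline to month 3 or 6:** the loss is understated, which works against the device.
- **Baseline to month 9 or 12:** there is no saline at either end, so there is no effect.
- **Month 6 to month 9 or 12:** the saline disappears at removal, so regain is understated. A descriptive account of whether loss is sustained would look slightly too good.
- **The 10% responder count, if read at month 6:** a subject whose true loss is just above 10% is counted as a failure. With 12 subjects, each one is 1/12 = 8.3 percentage points of the responder rate.

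**Working it through.** The plan states no figure for this effect, so there is nothing to reproduce. The size follows from these inputs.

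**Inputs**

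- Fill volume: 0.55 L (5.1) to about 0.60 L (5.4). Density is taken as about 1.0 kg/L. The shell weight is not given and is ignored.
- Baseline weight: not given. BMI is taken as 35 to 55, the range cited in section 4. Height of 1.60 to 1.80 m is an assumption.
- Mean TBWL at 6 months: 13.16% (1.5.3). An SD of 5 to 8 percentage points (pp) and a normal distribution are assumptions.

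**Step 1: mass.** 0.55 to 0.60 L × 1.0 kg/L = 0.55 to 0.60 kg.

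**Step 2: baseline weight = BMI × height².** Low: 35 × 1.60² = 89.6 kg. High: 55 × 1.80² = 178.2 kg.

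**Step 3: understatement of TBWL = fill mass / baseline weight.** Low: 0.55 / 178.2 = 0.31 pp. High: 0.60 / 89.6 = 0.67 pp. Before any offset, a subject must truly lose between 10 + 0.31 = 10.31% and 10 + 0.67 = 10.67% to register 10%.

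**Step 4: responder count at month 6.** A subject with true loss between 10% and 10% + s is misclassified, where s is the understatement. The probability is p = Φ((10 + s − 13.16)/SD) − Φ((10 − 13.16)/SD), and the expected number among 12 subjects is 12p.

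| s (pp) | SD (pp) | p | 12p |
|---|---|---|---|
| 0.31 | 8 | 0.3608 − 0.3464 = 0.0144 | 0.17 |
| 0.67 | 5 | 0.3092 − 0.2637 = 0.0455 | 0.55 |

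The expected shift is roughly 0.2 to 0.5 of a subject.

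This treats 13.16% as true body-mass loss. If the pooled figure already carries balloon mass, the true mean is 13.16 + s, and p becomes Φ((10 − 13.16)/SD) − Φ((10 − s − 13.16)/SD). That gives 0.3464 − 0.3322 = 0.0142 (0.17 subjects) and 0.2637 − 0.2218 = 0.0419 (0.50 subjects), so the conclusion does not change.

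**Step 5: change after removal.** Month 6 TBWL is low by s and month 9 or 12 TBWL is not, so a month 6 to month 9 or 12 change looks better by the same 0.31 to 0.67 pp.

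**Step 6: choice of fill figure.** A difference of 0.05 kg is worth 0.05 / 178.2 = 0.03 pp to 0.05 / 89.6 = 0.06 pp.

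**The case against.** The strongest reply is that the effect is small, runs against the device where the plan actually tests, and sits in a 12-subject pilot that is mainly descriptive. That stands. The bias cannot create a false positive at month 3 or 6, and the baseline-to-month-12 test, a natural reading of sustained loss, is unaffected. Section 7 specifies no month 6 to month 12 contrast; the artefact enters only if the report makes one, which the third aim invites but does not require.

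The net month 6 bias is also uncertain. The 48-hour liquid diet and the fast may lower a weight taken on the day of removal. The documents give no figure for this, it depends on scheduling, and it does not apply at month 3.

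One could argue that section 5.4, which lists a weight at the time of removal, means after removal. Footnote 8 ties the weight to the exam and the exam comes first, so this reading is weak; month 3 is unaffected by it.

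A reader might infer three stronger things that the documents do not support:

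- **That the fill hides a known share of an expected regain.** The fall from 13.16% to 11.27% is a difference between two pooled estimates. Section 1.4 gives 95% intervals of 12.37 to 13.95 and 8.17 to 14.36, which overlap. The estimates are not shown to come from the same studies, they may already include balloon mass, and the protocol nowhere states an expected regain.
- **That misclassification of at least one subject is a substantial risk.** Any such probability rests on an SD that the documents do not give. The expected count is a fraction of one subject.
- **That the fill volume goes unrecorded, or that the two fill figures are a serious conflict.** Section 5.8.3 and Table 3 do not claim to list every field, and the procedure note may hold the volume. The two figures differ by only 0.03 to 0.06 pp.

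**Conclusion.** The point holds as a minor one. Followed as written, the plan analyses month 3 and month 6 weights that include about 0.55 to 0.60 kg of saline in subjects who still have the balloon. Gross TBWL at those visits is understated by about 0.3 to 0.7 pp, given BMI 35 to 55 and height 1.60 to 1.80 m. The baseline-to-month-9 and baseline-to-month-12 tests are sound in this respect.

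Two results are exposed: the 10% responder count if read at month 6, and any comparison of month 6 with month 9 or 12. The size in the responder count depends on the assumed SD and normality, and the month 6 figures are gross of the diet and fast. The documents do not support reading this as an inflated efficacy claim or an invalid 12-month result.

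**What to change.** 1. Record the instilled volume for each implantation, including replacements under section 6.6, as a study data item.
2. In section 7, report month 3 and month 6 TBWL and the responder rate with and without subtraction of the fill mass, applied by balloon status at each weighing. Subtract nothing after early removal. If deflation or leakage is found, flag the weight rather than subtract the full fill, which would overstate the loss.
3. Use the corrected month 6 weight for any comparison with months 9 and 12.
4. Note whether the month 6 weight was taken during the liquid diet or fast.

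As a side point, make the fill figures in 5.1 and 5.4 agree.

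The cost is one added data field for the volume, a note with the month 6 weight, one extra analysis and a few sentences of text. Visits, procedures and sample size do not change.
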